#### **2.4.3 Potential Benefits of the Proposed Research to Research Participants and Others**

Successfully assisting people who smoke to quit would have significant positive benefits to their health. Overall, participants assigned to either of the two interventions have the potential to benefit by quitting smoking and the potential short and long term health benefits of quitting. We believe the low risks and non-invasive nature of the proposed research are greatly outweighed by the potential benefits to participants and others.

#### **2.4.4 Knowledge to be Gained**

Our QuitBot project has potential to develop an effective, resource-sensitive public health intervention for smoking cessation while advancing research on CAs and the science of communication in technology. This innovative project shows exciting promise for cost-effectively improving the success rates of cessation, and thereby lowering healthcare costs and reducing premature tobacco-related deaths on a population level. Given the low and reasonable risks to participants, we believe the potential benefits and knowledge to be gained outweigh the risks.

## **3.0 OVERVIEW OF CLINICAL TRIAL**

### **3.1 Study Objectives**

#### **3.1.1 Primary Objective**

The primary objective is to conduct a randomized controlled trial of QuitBot (n = 823) versus SmokefreeTXT (SFT) (n = 823), in order to determine whether QuitBot provides higher quit rates than SFT. The primary endpoint is 30-day biochemically confirmed cigarette smoking cessation at 12 months after randomization. Secondary endpoints are 30-day biochemically confirmed cigarette smoking cessation at 3 and 6 months after randomization.

#### **3.1.2 Secondary Objectives**

One secondary objectives is to determine whether QuitBot versus SFT operates according to therapeutic mechanisms of change, where cessation outcomes are significantly mediated by therapeutic alliance processes and engagement indicators in a serial multiple mediator model, which will show how CAs work and identify communication processes needing further targeting. Another secondary objective is to determine whether QuitBot is cost-effective vs. SFT), as measured by cost per quitter, cost per life year gained, and cost per quality-adjusted life year (QALY) gained. Additional objectives are to explore whether these baseline factors moderate the cessation outcomes of QuitBot, as compared to SFT: (a) trust, (b) social support, (c) demographics (e.g., sex).

### 3.2 Study Population

Adult male and female daily smokers (healthy volunteers) who currently smoke and want to quit in the next 30 days.

### 3.3 Study Design

We will conduct a fully-powered two-arm parallel randomized controlled trial comparing QuitBot to SmokefreeTXT (SFT). Based on evidence from text messaging trials meta-analyses [1], we will stratify randomization on biological sex (male vs. female), heaviness of smoking index score ( $\leq 4$  vs  $>4$ ), and percent confidence in being smoke-free in 12 months ( $\leq 70\%$  vs.  $>70\%$ ). Moderators will be measured at baseline, mediators at 3 and 6 months post randomization, and cessation and cost-effectiveness outcomes at 3, 6, and 12 months post randomization.

#### 3.3.1 Primary Endpoint

The primary endpoint is 30-day biochemically confirmed cigarette smoking cessation at 12 months after randomization.

#### 3.3.2 Secondary Endpoint

Secondary endpoints are 30-day biochemically confirmed cigarette smoking cessation at 3 and 6 months after randomization.

**3.4 Estimated Accrual:** 1520 participants. **Actual Accrual:** 1647 participants.

**3.5 Name of Sponsor/Funding Source:** NCI, NIH R01CA247156

## 4.0 SAFETY CONSIDERATIONS

### 4.1 Stopping Rules

#### 4.1.1 Stopping Rules for the Individual Participant

We have an established protocol in place with a referral policy for the clinical management of these participants with active suicidal/homicidal ideation.

#### 4.1.2 Stopping Rules for the Specific Study

Were the Fred Hutch's IRB or Clinical Trial's Office to issue a temporary or permanent suspension of the trial, the Principal Investigator will comply and immediately contact the trial's project officer. A Data Safety Monitoring Board will not be required since this is a minimal risk behavioral intervention.

Outside of the IRB or CTO's suspension decisions, there are no formal stopping rules including statistical and administrative procedures for early termination, because this is a remote, digital intervention for behavior change. Including such rules in this type of trial would yield a study that was inconclusive about the risks versus benefits of the treatments [127].

## 5.0 SUBJECT ELIGIBILITY

### 5.1 Inclusion Criteria

Inclusion criteria: (1) age 18 or older, (2) smokes at least one cigarette a day for the past 12 months, (3) wants to quit cigarette smoking within the next 30 days (consistent with text messaging intervention trials [1, 2]) (4) if concurrently using any other nicotine or tobacco products, wants to quit using them within the next 30 days, (5) interested in learning skills to quit smoking, (6) willing to be randomly assigned to either intervention, (7) resides in US, (8) has at least daily access to their own smartphone, (9) has text messaging on their smartphone and knows how to download a smartphone application (criterion 8 and 9 are needed minimum requirements to receive each interventions' content), (10) willing and able to read in English, and (11) not using other smoking cessation interventions. (This eligibility requirement helps ensure results are due to the treatments we recommend rather than those that participants are doing on their own.) Participants not eligible for were given the smokefree.gov website and 800-QUIT-NOW to reach their state's quitline.

### 5.2 Exclusion Criteria

Exclusion criteria: the reverse of the inclusion criteria.

## 6.0 SUBJECT REGISTRATION

For this trial, we will follow the QuitBot pilot RCT registration process, which was based on our successful WebQuit R01 protocol [84]. First, we will use our registration website to provide information about the study, FAQs, a brief video describing the study, information about the study team and Fred Hutch, and a portal to the informed consent form, screening, and baseline surveys. Second, collaborating with the Fred Hutch Communications Department, we will design Facebook and Google online ads for referring potential participants to the registration website. We will use our successful three-part strategy to register at least 30% minorities (the QuitBot pilot RCT had 28% minority): (1) use culturally-relevant online ads and enrollment website content targeted to minority smokers; (2) reaching out to minority-specific media newswire services to publicize the study; (3) program the registration website to limit non-minority registration to 70% and continue registration until the minority registration goal of at least 30% is reached. We will use a very similar 3-part strategy to register at least 40% men (the QuitBot pilot RCT had 33% men) and 12% age 65 and over.

We will use the registration protocol from the QuitBot pilot RCT, which was based on our WebQuit R01 protocol [85]. Specifically, those who screen eligible in the registration website and provide their email address will be instantly sent an email (and two reminders over a 14-day period) inviting them to complete a secured online survey to provide informed consent and complete the baseline assessment. To deter fraud, we will use (1) CAPTCHA authentication, (2) IP addresses that were previously used or suspicious will cause ineligibility, and (3) research staff will call participants if survey response times, email, or preferred communication method appear suspicious. Those not completing the online registration process within 14 days will be sent an email notifying them that they were not registered and provide both the smokefree.gov website and the 800-QUIT-NOW phone number. Those completing the registration process and randomized will be emailed a secured link connecting them to QuitBot or to SFT.

**Feasibility of data collection:** all of these methods have proven feasible in our published trials [84] and in our pilot trials, including the QuitBot pilot trial described in section 2.3 Clinical Data to date.

**7.0 TREATMENT PLAN**

The treatments in this study are remote digital interventions, delivered on smartphones and personal computers (i.e., the terms “inpatient” and “outpatient” do not apply here.) Additionally, descriptions will not include in-patient administrations drug-specific specifications (e.g., toxicities, prophylaxis, interactions, etc.) Specifically, participants will be randomized to either the QuitBot CA intervention or the SmokefreeTXT intervention.

QuitBot CA intervention: following randomization, participants in the CA arm will be sent a secured link to connect them to QuitBot by downloading and logging into the app hosting the CA. The QuitBot program consists of 42 days of 3 to 5-minute focused conversations (one conversation per day) over two phases: 14 days pre-quit and 28 days post quit. The content matches that of SFT, and follows US Clinical Practice Guidelines for cessation intervention [79]. The program content is presented as a continuous conversation, built on user input (e.g., stated motivations to quit, triggers to smoke, number of cigarettes smoked) from prior conversations. The program is proactive: at the user’s preferred time, QuitBot provides daily prompts to start a 3-5 minute structured text conversation—e.g., “Hi Alex, are you free to chat?” And on-demand/anytime, the user can get help with an urge, mood, and slips.

Smokefree comparison intervention: for initial evidence of whether CA is a fundamental shift beyond text messaging, SmokefreeTXT (SFT) is the ideal comparison. A 42-day program, SFT is the most widely accessible text messaging program in the US. It is non-proprietary and free to the public, thereby providing maximal accessibility and replicability. Daily messages are sent about the importance of quitting smoking, setting a quit date, preparing to quit, quitting, and maintaining abstinence. Daily messages check in about quit status. Three keywords can be sent by users to receive anytime help: “CRAVE” (on how to cope with urges), “MOOD” (on how to cope with moods triggering smoking), and “SLIP” (on how to cope with lapses). See Figure 3 for sample message. NCI’s SFT contractor (ICF International) provided us the full content of SFT so that we could internally host a secured private version for research. For blinding, the intervention was called “QuitBot.” Comparisons between QuitBot and SFT are shown in Table 2. In both SFT & QuitBot, participants receive two prompts per day (three on the quit day), with those not responding to prompts continuing where they left off.

[figure not shown]
**Table 2. Comparison of Conversational Agents (CAs) with Text Messaging Interventions.**

Engagement Feature	CA	Text
Personified digital coach (e.g., has name, background, and story)	Yes	No
Coach responds to user’s natural language (e.g., word choice, semantics)	Yes	No
Tailors responses to user’s unique motivations, triggers, and barriers to behavior change	Yes	No

Expresses empathy to user	Yes	No
Reflectively listens	Yes	No
Provides self-disclosures tailored to user's disclosures	Yes	No
Engages in social dialogue (e.g., "How are you?")	Yes	No
Provides meta-relational communication (i.e., talk about relationship)	Yes	No
Provides empirically supported behavior change content	Yes	Yes
Provides multiple short messages throughout the day or week	Yes	Yes
To operate, requires text messaging pricing plan (e.g., unlimited, limited, per-message)	No	Yes 

 In the US, text messaging cessation interventions require a cellular texting plan [3]

### Experimental Design Schema

#### 7.1 Duration of Therapy

Both therapies (the digital intervention programs) consist of 42 days of smoking cessation content.

#### 7.2 Duration of Follow-Up

The follow-up period lasts for 12 months and consists of three surveys. We will follow the 3, 6, and 12-month outcome survey data collection protocol we have used in four NIH trials (R01CA166646; R01CA192849; R01DA038411; R21DA030646). Follow-up data will be collected by our survey research unit that will be (1) blind to random assignment and (2) collecting cessation outcome data outside of the intervention. The online-telephone-mailed sequence protocol is as follows: Day 0: First email invitation with link to secured online version of survey; Day 7: Second email invitation with link to online survey; Days 10 to 18: Eight attempts to complete telephone version of survey (one call per day from a trained surveyor); Day 19: Send a paper version of the survey via US mail. Participants receive \$25 for survey completion. As proven successful in our prior trials, we will: (1) mail a \$2 pre-incentive letter (noncontingent incentives increase retention [106]) 7 days before the first online survey invitation (i.e., Day -7); (2) provide a \$10 bonus incentive (\$10 + \$25 = \$35) for completing the online survey within 24 hours; and (3) send a second copy of the mailed survey 10 days after the first mailing (i.e., Day 29). Based on our recent large RCT comparing two digital interventions [85], we estimate an 85% overall survey response rate [84]. In that RCT, 92% of those who completed the 12-month outcome survey responded online [84]. We thus expect about 92% of survey completers will do so online and thus minimize survey mode bias. Nonetheless, we will examine if mode of survey completion is associated with the cessation outcome.

Each assessment timepoint (at 3, 6, and 12 months) has a 90-day time window from when the follow up sequence begins: from Day 0, with the first email invitation, and then for 61 days after the second copy of the mailed survey is sent on Day 29, to allow for delayed responses. On Day 90, the collection window is closed. Any assessments returned after the window is closed are not included in the assessment data set for analysis.

**Feasibility of data collection:** all of these methods have proven feasible in our published trials [84] and in our pilot trials, including the QuitBot pilot trial described in section 2.3 (Clinical Data to date.) For example, the outcome data collection protocol has obtained 85-90% follow up in our previous studies [84].

Participation is considered ended after completion of the final survey.

## 8.0 ADVERSE EVENTS

### 8.1 Adverse Event

According to ICH guidelines (Federal Register. 1997; 62(90):25691-25709) and 21 CFR 312.32, IND Safety Reports, and ICH E2A, Definitions and Standards for Expedited Reporting, an adverse event is defined as follows:

An adverse event is any untoward medical occurrence in a clinical investigation subject administered a medicinal product and which does not necessarily have a causal relationship with this treatment. An AE can therefore be any unfavorable and unintended sign (including an abnormal laboratory finding), symptom, or disease temporally associated with the use of a medicinal product, whether or not considered related to the medicinal product.

Abnormal laboratory values for laboratory parameters specified in the study should not be recorded as an adverse event unless an intervention is required (repeat testing to confirm the abnormality is not considered intervention), the laboratory abnormality results in a serious adverse event or the adverse event results in study termination or interruption/discontinuation of study treatment.

Medical conditions present at screening (i.e., before the study treatment is administered) are not adverse events and should not be recorded on adverse event pages of the CRFs. These medical conditions should be adequately documented on the subject chart. However, medical conditions present at baseline that worsen in intensity or frequency during the treatment or post-treatment periods should be reported and recorded as adverse events.

For this trial, an example of an unexpected event that is not adverse is a participant who has become very unhappy with trial procedures. Adverse events (AEs) are any untoward occurrence with a trial participant whether or not it can be considered to be related to their smoking cessation intervention (the QuitBot CA or SmokefreeTXT programs). An example of an adverse event in this trial could include an increase in depressive symptoms. Serious adverse events (SAEs) include any AE that results in death, a real risk of dying, inpatient hospitalization, persistent or significant disability/incapacity, or AEs that require intervention to prevent permanent impairment or damage. In this trial, an example of a serious adverse event would be a suicide attempt.

UEs, AEs, and SAEs will be reported to the Principal Investigator as soon as staff members are aware of them. If there is any doubt as to whether an event qualifies as a UE, AE, or SAE, staff members will be trained and encouraged to err on the side of caution – and to bring the event to the Principal Investigator's attention for review.

#### Serious Adverse Event

An adverse event should be classified as an SAE if it meets one of the following criteria:

Fatal	Adverse event results in death.
Life threatening:	The adverse events placed the subject at immediate risk of death. This classification did not apply to an adverse event that hypothetically might cause death if it were more severe.
Hospitalization:	It required or prolonged inpatient hospitalization. Hospitalizations for elective medical or surgical procedures or treatments planned before enrollment in the treatment plan or routine check-ups are not SAEs by this criterion. Admission to a palliative unit or hospice care facility is not considered to be a hospitalization.
Disabling/incapacitating	Resulted in a substantial and permanent disruption of the subject's ability to carry out normal life functions.
Congenital anomaly or birth defect:	An adverse outcome in a child or fetus of a subject exposed to the molecule or treatment plan regimen before conception or during pregnancy.
Medically significant:	The adverse event did not meet any of the above criteria, but could have jeopardized the subject and might have required medical or surgical intervention to prevent one of the outcomes listed above.

### 8.2 Unexpected Adverse Event

An unexpected adverse event is defined as an event that has a nature or severity, or frequency that is not consistent with the applicable investigator brochure, or the prior medical condition of the subject or other treatment given to the subject. "Unexpected," as used in this definition, refers to an adverse drug experience that has not been previously observed and

reported in preclinical or clinical studies rather than an experience that has not been anticipated based on the pharmacological properties of the study drug.

### 8.3 Monitoring and Recording Adverse Events

All AEs will be assessed by the investigator or qualified designee and recorded in the CRFs. The investigator should attempt to establish a diagnosis of the event on the basis of signs, symptoms and/or other clinical information. In such cases, the diagnosis should be documented as the adverse event and/or serious adverse event and not described as the individual signs or symptoms. The following information should be recorded:

- Description of the adverse event using concise medical terminology
- Description as to whether or not the adverse event is serious, noting all criteria that apply
- The start date (date of adverse event onset)
- The stop date (date of adverse event resolution)
- The severity (grade) of the adverse event
- A description of the potential relatedness of the adverse event to study drug, a study procedure, or other causality
- The action taken due to the adverse event
- The outcome of the adverse event

### 8.4 Attribution of an Adverse Event

The Principal Investigator, in consultation with the Co-Investigators and Project Manager, will decide if a UE should be classified as an AE. If an event is classified as an AE, further attribution will be determined, as follows:

- Related – AEs that are definitely, probably, or possibly related to the smoking cessation interventions (the QuitBot CA or SmokefreeTXT programs).
- Not Related – AEs that are doubtfully related or clearly not related to the smoking cessation intervention (the QuitBot CA or SmokefreeTXT programs).

### 8.5 Adverse Event Recording Period

Throughout the study, the Principal Investigator, Co-Investigators, and Project Manager will monitor participants for adverse events and protocol compliance. The Project Manager will complete monthly reports on participant progress and status, any adverse events, and any protocol deviations. Protocol adherence will be monitored by the PI.

Study staff will be trained, and required, to report all unexpected and adverse events to the PI during the study recruitment, intervention, and follow up periods. Adverse events beyond what would be expected in the course of smoking cessation will be reported to the Fred Hutch's IRB in accordance with Fred Hutch policy.

### 8.6 Adverse Event Reporting Requirements

1. SAEs: For AEs meeting the criteria for an SAE, regardless of its attribution, a Fred Hutch SAE Report form will be completed. The SAE Report form will be sent by the Principal Investigator to the IRO office within 24 hours of the internal report. All available information will be submitted. Should additional information become available after the initial report, a revised report will be submitted within 15 days.
2. AEs that do not meet the criteria for SAE: For these events, the Principal Investigator or the Study Coordinator will complete and submit a Fred Hutch Adverse Event Reporting form within ten (10) calendar days of learning of the events.
3. UEs that do not meet the criteria for AEs: For these events, the Study Coordinator will complete and submit a Fred Hutch UE Reporting Form within ten (10) calendar days of learning of the events.

Classification		Reporting Time	Reporting Action	Contact Information
SAE	Fatal or life-threatening	Within 24 hours of research team* awareness	Email notification to Sponsor's Medical Monitor	Medical Monitor email: [contact] ISIOC email: [contact]
	All SAEs	Within 2 business days of research team* awareness	Submit completed Institution-Sponsored IND SAE Reporting	ISIOC [contact]

			Form signed by PI or designated sub-Investigator	ISIOC email: [contact]
Non-serious AE		Per CRF completion guidelines	Record information on appropriate CRFs	N/A

\*Research team is defined as the individuals listed on the delegation of authority log. Physicians listed on the study's delegation of authority log as attending physicians delegated authority to administer informed consent will not be considered part of the research team unless additional responsibilities related to the conduct of the study have been delegated to them by the Principal Investigator.

## 9.0 DATA AND SAFETY MONITORING PLAN

Institutional support of trial monitoring will be in accordance with the FHCRC/University of Washington Cancer Consortium Institutional Data and Safety Monitoring Plan. Under the provisions of this plan, FHCRC Clinical Research Support (CRS) coordinates data and compliance monitoring conducted by consultants, contract research organizations, or FHCRC employees unaffiliated with the conduct of the study. Independent monitoring visits occur at specified intervals determined by the assessed risk level of the study and the findings of previous visits per the institutional DSMP.

In addition, protocols are reviewed at least annually and as needed by the Consortium Data and Safety Monitoring Committee (DSMC), FHCRC Scientific Review Committee (SRC) and the FHCRC/University of Washington Cancer Consortium Institutional Review Board (IRB). The review committees evaluate accrual, adverse events, stopping rules, and adherence to the applicable data and safety monitoring plan for studies actively enrolling or treating subjects. The IRB reviews the study progress and safety information to assess continued acceptability of the risk-benefit ratio for human subjects. Approval of committees as applicable is necessary to continue the study.

The trial will comply with the standard guidelines set forth by these regulatory committees and other institutional, state and federal guidelines.

Data and safety monitoring reports will be reviewed in the course of the trial on a monthly basis by [name]. A Data and Safety Monitoring Board will not be required since this is a minimal risk behavioral intervention, but twice a year [name] and the Co-Investigators will review the study protocol and study data concerning registration, randomization, retention, compliance, form completion, gender and minority inclusion, intervention effects, safety, protocol violations, adverse events, and any other relevant topics in order to assure participant safety and study integrity. They will also review interim analyses of outcome data to determine whether the trial should continue as originally designed, should be changed, or should be terminated based on these data. If in-person meetings are not possible, meetings will be held by conference call. More frequent meetings will be convened as necessary.

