11.5 Sample Size and Power

We determined sample size for binomial proportions aimed at 80% power for Primary Objective 1 using the following parameters: (1) randomized to one of the two interventions; (2) conservative 12-month outcome survey response rate of 85%, based on our most recently published large RCT comparing two digital interventions [84]; (3) 80% completion rate of biochemical verification [103, 104]; (4) intent-to-treat analysis where, as standard in digital intervention smoking cessation trials, all those with missing data (including missing biochemical data) are coded as smokers [1, 121]; and (5) two-sided test with  $\alpha = .05$ . We adjusted all power analyses for expected non-response rates and biochemically-confirmed cessation rates so that outcomes would not be inflated.

Power for Objective 1: Objective 1 will compare 12-month quit rates between QuitBot vs. SFT. Projected quit rates at 12-month follow-up were conservatively calculated using (1) quit rates at 3-month follow-up in our pilot RCT, along with (2) well-established relapse curves, which provide a data-derived estimate (i.e., 20-35%) of the rate of decay of intervention effects by 12-month follow-up [90, 91, 122]. We estimated a relapse of 27% (between 3 and 12 month-follow-up) and survey response and biochemical verification completion rates of 85% and 80%, respectively. The 12-month quit rate for SFT is conservatively estimated as 9.3%, as consistent with the projected SFT 12-month relapse rates from the pilot RCT and the 8.4% average quit rate from the most recent meta-analyses [1, 2, 18-21]. As shown in Table 5, obtaining 80% power to significantly detect a quit rate as low as 13.9% for QuitBot (vs. 9.3% for SFT) requires 1,520 randomized participants, with 760 in each study arm.

Table 3. Objective 1 Sample Size Estimates.

	Projected relapse rate				
	20%	25%	27%	30%	35%
	QuitBot 12-month follow-up 30-day point prevalence quit rate				
	15.2%	14.3%	13.9%	13.3%	12.4%
Total in each arm	484	653	760	983	1,579
Total randomized	968	1,306	1,520	1,966	3,158

This very conservatively estimated 13.9% quit rate would have high public health impact—49% higher impact than the projected 9.3% quit rate for SFT and 65% higher than the average 8.4% quit rate observed in text messaging interventions [1, 2, 18-21].

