### 11.6 Stopping Rules

Were the Fred Hutch's IRB or Clinical Trial's Office to issue a temporary or permanent suspension of the trial, the Principal Investigator will comply and immediately contact the trial's project officer. A Data Safety Monitoring Board will not be required since this is a minimal risk behavioral intervention.

Outside of the IRB or CTO's suspension decisions, there are no formal stopping rules including statistical and administrative procedures for early termination, because this is a remote, digital intervention for behavior change. Including such rules in this type of trial would yield a study that was inconclusive about the risks versus benefits of the treatments [127].

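### Section 9.0 lets the investigators change or end the trial on interim outcome data, while the stopping sections disclaim any such procedure and no alpha is reserved for it

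*Combined protocol and SAP*

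**What the plan says.** Section 9.0 dispenses with a dedicated board ("A Data and Safety Monitoring Board will not be required since this is a minimal risk behavioral intervention") and substitutes a twice-yearly review by the study lead and the Co-Investigators. Besides operational items, the topics include "intervention effects, safety, protocol violations, adverse events". The same people are then to "review interim analyses of outcome data to determine whether the trial should continue as originally designed, should be changed, or should be terminated". The number of looks is open: "More frequent meetings will be convened as necessary".

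Sections 4.1.2, 11.6 and 13.0 repeat one paragraph: apart from a suspension by the IRB or the Clinical Trials Office, "there are no formal stopping rules including statistical and administrative procedures for early termination". The reason given is that such rules would leave a trial of this type inconclusive.

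Section 11.5 describes a sample size "aimed at 80% power for Primary Objective 1" with a two-sided alpha of .05. Neither Section 11.2 nor 11.5 mentions an interim analysis, an information fraction, a boundary or alpha spending. Section 11.7 describes participants and outcome assessors as blind, and nobody else.

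**The concern.** Section 9.0 sets up a recurring procedure for altering or ending the trial on outcome data. The other three sections say no statistical or administrative procedure for early termination exists, and argue that one would be harmful. Both cannot govern the same trial.

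At stake is what the final p-value means. If the trial could stop for success, or be redesigned, on unadjusted comparative results, the nominal 0.05 is not the true error rate. The reviewers also run the trial, and the plan does not say that what they see is pooled over arms. A reader of the final result cannot tell from the plan whether comparative cessation data were seen along the way, or what was done about them.

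**Working it through.** **1. Is any alpha held back for interim looks?** Inputs from Section 11.5: 9.3% (SFT) versus 13.9% (QuitBot), two-sided alpha 0.05, power 80%, 760 per arm. With the pooled-variance formula and mean rate 0.116:

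n = [1.96·√(2 × 0.116 × 0.884) + 0.8416·√(0.093 × 0.907 + 0.139 × 0.861)]² / (0.139 − 0.093)²

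= (0.8876 + 0.3802)² / 0.002116 = 1.6072 / 0.002116 = 759.6, so 760 per arm.

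This reproduces the plan's figure exactly, and the other four columns of Table 3 also reproduce (484, 653, 983, 1,579). The trial is therefore sized as a fixed design with one analysis, and nothing is reserved.

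**2. How many looks could carry primary-endpoint data?** The synopsis gives a 30-month trial and a 12-month endpoint. Twice-yearly meetings fall at months 6, 12, 18, 24 and 30. No 12-month outcome exists at months 6 or 12. Accrual time is not stated, so I assume it is roughly uniform.

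- Accrual over 18 months: the fraction with 12-month data is (18 − 12)/18 = 1/3 at month 18, (24 − 12)/18 = 2/3 at month 24, and 1 at month 30.
- Accrual over 15 months, which leaves room for the 90-day survey window in Section 7.2: (18 − 15)/15 = 0.2, (24 − 15)/15 = 0.6, and 1.

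That is at most three scheduled analyses including the final one, or two if only one meeting looks at the endpoint.

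**3. Type I error if |Z| > 1.96 counts as success at any analysis.** The statistics are jointly normal with correlation √(t_j/t_k) for t_j < t_k. The error is 1 − P(all |Z_k| < 1.96).

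| Analyses | Information fractions | Correlations | Overall type I error |
|---|---|---|---|
| 1 | 1 | – | 5.0% |
| 2 | 1/2, 1 | 0.707 | 8.3% |
| 3 | 1/3, 2/3, 1 | 0.707, 0.577, 0.816 | 10.7% |
| 3 | 0.2, 0.6, 1 | 0.577, 0.447, 0.775 | 11.5% |

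**4. What control would cost at the planned size** (equally spaced analyses, 760 per arm):

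| Scheme | Final nominal level, 2 / 3 analyses | Power, 2 / 3 analyses |
|---|---|---|
| O'Brien-Fleming | 0.048 / 0.045 | 79.7% / 79.3% |
| Pocock | 0.029 / 0.022 | 75.6% / 73.4% |

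With a Haybittle-Peto rule (interim p<0.001, final test left at 0.05) the overall error is 5.02% with two analyses and 5.05% with three.

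**The case against.** The strongest defence is that the stopping sections deny only *formal* rules, so Section 9.0 may describe an informal review, and that its stated purpose is participant safety and study integrity. Looks for harm or futility do not raise the type I error, and nothing in the plan says that success would be declared at an interim p<0.05. This stands in part: the inflation is conditional. It does not remove the conflict, because the repeated paragraph excludes statistical and administrative procedures for early termination, and Section 9.0 does not confine itself to harm or futility.

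Four stronger readings are tempting but unsupported.

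- *An error rate near 14%.* Five equally spaced unadjusted looks, twice a year for 30 months, would give 14.2%. But the first two meetings precede any 12-month outcome. Five would need unscheduled meetings, or looks at the 3- and 6-month endpoints, which the primary 0.05 does not cover.
- *Enrolment rose from 1,520 to 1,647 because results were seen.* No text links the two. Section 6.0 offers a possible reason unrelated to outcomes: registration stays open until the minority goal is met, with a similar strategy for men and for people aged 65 and over.
- *There is no independent oversight.* Section 9.0 provides for at least annual review by the DSMC, SRC and IRB, and for monitoring by people outside the study. The narrower statement holds: none of them is assigned the interim outcome analysis.
- *Follow-up could be steered.* Section 7.2 fixes the contact sequence and gives it to a survey unit blind to assignment, which largely guards against this.

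By-arm display is also an inference. A review of intervention effects suggests a comparison, but Section 9.0 does not say how results are shown.

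**Conclusion.** The point holds as a contradiction with a statistical consequence. Section 9.0 must be reconciled with Sections 4.1.2, 11.6 and 13.0, which count as one statement made three times. As written, the plan does not control the type I error of its primary test.

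The size is about 8% to 12% instead of 5%. It rests on three assumptions: efficacy is claimed at an unadjusted p<0.05 at any look, there are two or three primary-endpoint analyses in total, and accrual is roughly uniform over about 15 to 18 months. If the looks served only harm or futility, there would be no inflation. If the design were changed on by-arm results, the error rate could not be calculated from the plan. The documents do not show that any look took place or influenced the trial. If none is made, 760 per arm and the 0.05 level stand unchanged.

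**What to change.** 1. In Section 9.0, delete the sentence on interim analyses of outcome data and remove *intervention effects* from the list of topics. Limit the investigators' reviews to safety and to accrual, retention and compliance pooled over arms.
2. State there that no by-arm cessation results are seen before the 12-month database is closed. Section 9.0 then agrees with 4.1.2, 11.6 and 13.0.
3. In Section 11.2, state whether any by-arm outcome look has already been made, when, by whom, and what was decided on it. Enrolment is recorded as complete, so this disclosure is what a reader of the final result most needs.
4. If an outcome look is to be kept, specify its timing, assign it to someone outside the study team, and give an alpha-controlling boundary in 11.2, with 4.1.2, 11.6 and 13.0 amended to match. Haybittle-Peto is one option among several and leaves the final test practically at 0.05.

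The cost is a few sentences and no change in sample size. The downside is that the investigators lose early sight of by-arm outcomes.
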